9.2 Clinical Laboratory Evaluations

Hematology and chemistry parameters will be summarized at baseline (prior to first dose) and last dose, as well as change from baseline to last dose. Tables (by dose groups) will present n, mean, median, minimum, and maximum at baseline, last dose, last day of 7-day safety follow-up period, 36 weeks PMA and change from baseline to last dose. A summary of result assessment shifts from baseline to last dose will be given for each dose group for each parameter. Each parameter will be coded as abnormal and clinically significant (“ABN, CS”) or abnormal and not clinically significant (“ABN, NCS”). The number and percentage of subjects in each dose group in each shift category from baseline to last dose will be shown for each parameter.

Laboratory values at baseline, last dose and changes from baseline to last dose will also be summarized descriptively by dose groups using box plots. The box will represent the 75th and 25th percentiles and the upper and lower whiskers will represent the 95th and 5th percentiles. Mean, median and outliers will be identified. On each box plot, the number available, mean and median will also be presented numerically.

This will be completed for hematology laboratory test (including platelets) and chemistry laboratory test (including alkaline phosphatase, bicarbonate, bilirubin (direct), bilirubin (total), bilirubin (indirect), BUN, caffeine, calcium (ionized), calcium (total), chloride, creatinine, magnesium, phosphorus, potassium, sodium).

The laboratory events of interest will be summarized by dose groups. The laboratory adverse events of interest are listed in Table 3. Any abnormal laboratory values indicating serum electrolytes, renal dysfunction and other dysfunction are captured as laboratory adverse events of interest.

Table 7: Laboratory event values [4]

Laboratory values	Adverse event	Serious adverse event
Serum electrolytes		
Hypernatremia(Sodium)	150–159 mmol/L	> 159 mmol/L
Hyponatremia(Sodium)	120–124 mmol/L	<120 mmol/L
Hyperchloremia(Chloride)	110–120 mmol/L	> 120 mmol/L
Hypochloremia(Chloride)	80–90 mmol/L	< 80 mmol/L
Hyperkalemia(Potassium)	7.0–7.9 mmol/L	>7.9 mmol/L
Hypokalemia(Potassium)	2.0–2.5 mmol/L	<2.0 mmol/L
High Bicarbonate levels (Bicarbonate)	30–45 mmol/L	> 45 mmol/L

Low Bicarbonate levels(Bicarbonate)	12–14 mmol/L	< 14 mmol/L
Hypercalcemia (iCa)	1.3–1.6 mmol/L	>1.6 mmol/L
Hypocalcemia (iCa)	0.7–1.05 mmol/L	< 0.7 mmol/L
Hypermagnesemia (Magnesium)	3.0–6.0 mg/dL	> 6.0 mg/dL
Hypomagnesemia (Magnesium)	1.0–1.5 mg/dL	< 1.0 mg/dL
Hypophosphatemia(Phosphorus)	1.0–3.0 mg/dL	<1.0 mg/dL
Hyperphosphatemia(Phosphorus)	10.5–12.5 mg/dL	>12.5 mg/dL
Hyperbilirubinemia (Bilirubin)	20–30 mg/dL	>30 mg/dL
Renal dysfunction (i.e. azotemia)		
Elevated BUN	60–100mg/dL	> 100 mg/dL
Elevated creatinine	1.5–2.5 mg/dL	> 2.5 mg/dL
Gastrointestinal		
Elevated alkaline phosphatase	1000–1400 U/L	>1400 U/L
Hematology		
Thrombocytosis(Platelets)	450–1000 × 10 ⁹ /L	>100010 × 10 ⁹ /L
Thrombocytopenia(Platelets)	50–100 × 10 ⁹ /L	<50 × 10 ⁹ /L

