9.3 Concomitant Medications of Interest

All concomitant medications, including intravenous potassium boluses or enteral electrolyte supplements, and treatments (including other diuretics) will be reported during the study drug administration period. All concomitant medications will be coded using the World Health Organization (WHO) drug classification system and presented by Anatomical Therapeutic Chemical Classification system first level (ATC1) drug classification and drug name. Frequency distributions of concomitant medications will be listed by ATC1 drug classification, drug name, and dose groups. Any diuretics used other than study furosemide during study period will be summarized separately. The cumulative dose, maximum daily dose and mean dose for caffeine at participant level will be summarized in mg/kg by dose groups. A listing of concomitant medications by participant will include start and end dates (or ongoing), and indication. Also, a listing of caffeine doses will be included.

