14.3 SAFETY			
14.3.1.1	Safety	Summary of Adverse Events by Dose Groups (including Summary of AEs, and SAEs)	16.2.8.1, 16.2.8.2, 16.2.8.3
14.3.1.2	Safety	Adverse Events by System Organ Class, Preferred Term and by Dose Groups	16.2.8.1
14.3.1.3	Safety	Serious Adverse Events by System Organ Class, Preferred Term and by Dose Groups	16.2.8.2
14.3.1.4	Safety	Serious Adverse Reactions by System Organ Class, Preferred Term and by Dose Groups	16.2.8.3
14.3.1.5	Safety	Adverse Events by System Organ Class, Preferred Term, Severity and by Dose Groups	16.2.8.1
14.3.1.6	Safety	Adverse Events by System Organ Class, Preferred Term, Relationship to Study Medication and by Dose Groups	16.2.8.1
14.3.1.7	Safety	Adverse Events Listed by Most Frequent Preferred Term and by Dose Groups	16.2.8.1
14.3.1.8	Safety	Summary of Special Safety Events of Interest by Dose Groups	16.2.8.4, 16.2.8.5, 16.2.8.6
14.3.2	Safety	Summary of Laboratory Events by Dose Groups	16.2.9.1, 16.2.9.2
14.3.3.1	Safety	Summary of Clinical Laboratory Hematology Measurements by Visit and Dose Groups (platelets)	16.2.9.1

14.3.3.2	Safety	Summary of Clinical Laboratory Serum Chemistry Measurements by Visit and Dose Groups (alkaline phosphatase, bicarbonate, bilirubin (direct), bilirubin (total), bilirubin (indirect), BUN, caffeine, calcium (ionized), calcium (total), chloride, creatinine, magnesium, phosphorus, potassium, sodium)	16.2.9.2
14.3.4	Safety	Summary of Concomitant Medications of interest by Drug Classification, Drug Name and Dose Groups	16.2.10
14.3.5	Safety	Summary of Physical Examination Findings by Body System and Dose Groups	16.2.11

Figure Number	Population	Table Title / Summary	Supports Table Number(s)
14.4.1	Safety	Box Plot of Hematology Laboratory Measurement by Visit and Dose Groups (platelets)	16.2.9.1
14.4.2	Safety	Box Plot of Each Chemistry Laboratory Measurement by Visit and Dose Groups (alkaline phosphatase, bicarbonate, bilirubin (direct), bilirubin (total), bilirubin (indirect), BUN, caffeine, calcium (ionized), calcium (total), chloride, creatinine, magnesium, phosphorus, potassium, sodium)	16.2.9.2
14.4.3	Safety	Patient Profile	16.2.1, 16.2.6, 16.2.8.5, 16.2.9.1, 16.2.9.2

Listing Number	Population	Listing Title / Summary	Supports Table Number(s)
16.2.1	All Participants	Final Study Disposition	14.1.1.1, 14.1.1.2
16.2.2	All Participants	Inclusion/Exclusion Criteria	N/A
16.2.3	Safety	Demographic Characteristics	14.1.2.1
16.2.4	Safety	Medical History	14.1.2.2

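### Laboratory change, shift and box-plot summaries stop at the last-dose value; no worst on-treatment value is summarised by dose group

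*SAP*

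**What the plan says.** Section 9.2 sets the laboratory displays as follows.

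- Change: "Hematology and chemistry parameters will be summarized at baseline (prior to first dose) and last dose, as well as change from baseline to last dose".
- Level tables: statistics "at baseline, last dose, last day of 7-day safety follow-up period, 36 weeks PMA and change from baseline to last dose". The two added time points both fall after treatment.
- Shifts, using the abnormal clinically significant / not clinically significant coding: "A summary of result assessment shifts from baseline to last dose will be given for each dose group for each parameter".
- Box plots: "Laboratory values at baseline, last dose and changes from baseline to last dose will also be summarized descriptively by dose groups using box plots".

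The same section plans a separate event summary: "The laboratory events of interest will be summarized by dose groups". On its scope it says: "Any abnormal laboratory values indicating serum electrolytes, renal dysfunction and other dysfunction are captured as laboratory adverse events of interest". The limits stand in a table captioned Table 7, which the text cites as Table 3. The output is Table 14.3.2, "Summary of Laboratory Events by Dose Groups".

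Section 9.3 has corrective treatment reported during the dosing period: "All concomitant medications, including intravenous potassium boluses or enteral electrolyte supplements". Section 3.1 gives a treatment period of 28 days.

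**The concern.** Describing safety is the primary objective, in a design that escalates dose across three cohorts. Section 9.3 provides for potassium boluses and electrolyte supplements being given while dosing continues, so a value can be abnormal in mid-course and normal by last dose. Such a value is absent from the change table, the shift table and the box plots.

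Last dose is also not a common time point. Section 8.1 distinguishes infants with under 7 days of study product from those with 7 to 28 days, so dose groups may be compared after different exposures.

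What is at stake is how clearly the report shows the size of on-treatment laboratory change by dose. Whether marked events are counted at all is not in doubt.

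**Working it through.** The SAP gives no figure on this point. Its only planning figures, in section 5, reproduce: 1 − 0.95^30 = 78.5% (stated 79%) and 1 − 0.95^90 = 99.0% (stated 99%). They concern the chance of seeing an event at least once. The point does not depend on them.

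**Step 1. Which group-level displays can show a disturbance corrected before last dose?**

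| Display | Can show it? |
|---|---|
| Change from baseline (9.2) | No, last dose only |
| Shift table (9.2) | No, last dose only |
| Box plots (9.2) | No, baseline and last dose only |
| Level tables (9.2) | No on-treatment point before last dose is named |
| Laboratory events (Table 14.3.2) | Yes, if a Table 7 limit is met |
| Adverse event tables (14.3.1.x) | Yes, if reported as an adverse event |
| Concomitant medications (Table 14.3.4) | Indirectly, through the corrective treatment |

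**Step 2. What do the Table 7 limits miss?** They are fixed values that do not refer to the infant's own baseline. The infants below are hypothetical; the limits are the SAP's.

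- Creatinine 0.5 rising to 1.4 mg/dL: change 1.4 − 0.5 = 0.9, ratio 1.4 / 0.5 = 2.8. The event range starts at 1.5, so this is no event.
- Creatinine 1.6 mg/dL at entry and unchanged on treatment: change 0. Only values above 1.7 are excluded (section 1.1), so the infant is eligible. The value lies within 1.5–2.5, so it meets the event limit.
- Potassium 2.6 mmol/L: the low ranges are 2.0–2.5 and below 2.0, so no event, wherever the infant started.
- Sodium 125 mmol/L: the low ranges are 120–124 and below 120, so no event.

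The creatinine pair shows that the event count can rank two infants in the opposite order to their on-treatment change.

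**Step 3. How likely is a last-dose display to catch a short episode?** This is an illustration only. Assume one episode of d days, starting on a uniformly placed day of T dosing days, with a sample at last dose. It is still present on the last day with probability d/T.

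| d (days) | T = 28 | T = 14 |
|---|---|---|
| 1 | 1/28 = 3.6% | 1/14 = 7.1% |
| 3 | 3/28 = 10.7% | 3/14 = 21.4% |
| 7 | 7/28 = 25% | 7/14 = 50% |

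Episode length and timing are assumptions. The figures describe the last-dose displays alone. They are not a loss from the report for episodes that meet a Table 7 limit or are reported as adverse events.

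**The case against.** A reader might infer that corrected disturbances vanish from the report, or that the treatment period is not summarised at all. The documents do not support either reading.

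- The laboratory-event summary is not tied to the last dose. A transient potassium of 2.3 mmol/L that is normal by last dose is counted.
- Under section 9.1, any change in routine laboratory values that the investigator considers clinically significant is an adverse event, with no numeric limit. Adverse events are tabulated by preferred term, severity, relationship and dose group.
- Electrolyte supplements are reported by dose group, so a group with many corrections would show there too.
- Section 7 plans chronological patient profiles, and listings 16.2.9.1 and 16.2.9.2 hold the measurements.
- Tables 14.3.3.1–14.3.3.2 and Figures 14.4.1–14.4.2 are titled by visit, so on-treatment visits may be intended.

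It would also be wrong to size the loss by comparing infants abnormal at any draw with those abnormal at the last draw. Being beyond a limit at any draw is what the event table already reports. Finally, a worst-value summary depends on treatment length too, and section 7 calls the analyses exploratory or descriptive.

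All of this stands, and it narrows the point without removing it. Event and adverse event tables give counts, not the size of a change from baseline. Profiles and listings give no comparison between dose groups. The table titles do not supply the visits that section 9.2 leaves unnamed. The any-abnormal sentence in 9.2 could be read more widely than the Table 7 limits, but the SAP does not say so.

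**Conclusion.** The point holds in a limited form. The change, shift and box-plot displays of section 9.2 use the last-dose value only. Two things are therefore missing at dose-group level: the size of the worst on-treatment change, and transient changes that neither meet a Table 7 limit nor are reported as adverse events.

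No count of affected infants can be derived, because the SAP gives neither the laboratory schedule nor expected abnormality rates. The conclusion assumes that samples are drawn during treatment before the last dose, and that the event summary applies the Table 7 limits. If the any-abnormal sentence has a wider meaning, fewer values are missed, but the size of change is still not summarised.

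This is a cheap improvement to the primary safety description. It does not mean that the plan hides marked events.

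**What to change.** In section 9.2, Tables 14.3.3.1–14.3.3.2 and Figures 14.4.1–14.4.2, keep the last-dose summaries and add the following beside them, by dose group: shift, and change from baseline, to the worst on-treatment value of each parameter. Define the window as first dose through last dose. Use both the minimum and the maximum where both directions matter, as for sodium and potassium.

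The worst value becomes more extreme with more draws and longer treatment. Report the number of draws and the days on drug by dose group in the same tables, so that a difference in extremes can be read against them.

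In the same edit, state which visits the by-visit outputs cover, whether laboratory events are limited to the Table 7 ranges, the time window and counting unit (infants or events) of Table 14.3.2, and correct the Table 3 / Table 7 reference.

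The cost is table programming and a few more pages of output. If on-treatment values are collected as assumed, no new data are needed and no planned analysis is removed.

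### Table 14.3.2 counts electrolyte events from blood values alone, so replacement given before a value reaches the event band attenuates the dose-safety relation

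*SAP*

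**What the plan says.** Section 9.2 plans the event summary: "The laboratory events of interest will be summarized by dose groups. The laboratory adverse events of interest are listed in Table 3". It defines the laboratory events by value: "Any abnormal laboratory values indicating serum electrolytes, renal dysfunction and other dysfunction are captured as laboratory adverse events of interest". The bands stand in the table that follows (labelled Table 7 although the text points to Table 3, which is a separate matter). For hypokalemia they are 2.0–2.5 mmol/L for an adverse event and below 2.0 mmol/L for a serious one. The output is table 14.3.2, "Summary of Laboratory Events by Dose Groups". Section 9.2 does not say how a value obtained under supplementation is read.

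The continuous summaries use few time points: "Hematology and chemistry parameters will be summarized at baseline (prior to first dose) and last dose, as well as change from baseline to last dose". The tables also show the end of follow-up and 36 weeks PMA.

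Section 9.3 covers replacement: "All concomitant medications, including intravenous potassium boluses or enteral electrolyte supplements, and treatments (including other diuretics) will be reported during the study drug administration period". The planned display is table 14.3.4: "Frequency distributions of concomitant medications will be listed by ATC1 drug classification, drug name, and dose groups". A participant listing (16.2.10) gives dates and indication. The same section plans a separate summary for other diuretics, and cumulative, maximum daily and mean doses in mg/kg for caffeine. Electrolyte supplements get neither.

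**The concern.** Describing safety is the trial's primary objective, and the length of the electrolyte list in 9.2 shows how much of that description rests on these events. A value-based count measures drug effect together with how actively falling values were corrected. If correction is more frequent where losses are larger, events are prevented mainly at the higher doses, and the gradient in table 14.3.2 is flatter than the drug's effect on electrolytes.

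Other laboratory outputs do not repair this. Baseline-to-last-dose summaries and shift tables also reflect corrected values. A worst on-treatment value would not recover an event that was prevented rather than missed.

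Table 14.3.4 holds the complementary information in a form that is hard to use here. It counts by ATC1 class and drug name, not by electrolyte. It does not separate supplements started after first dose from those already running at baseline. It is not read jointly with the laboratory events. The interim analyses in 4.2 tabulate laboratory adverse events by cohort and name no supplement summary, so the value-only counts may stand alone at those looks. The advancement rule in 4.1 counts Serious Adverse Reactions, so these rows do not drive escalation directly.

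**Working it through.** **1. The plan's own figures.** SAP section 5 gives 95% Wilson widths and detection probabilities. With z = 1.96, width = 2z·√(p(1−p)/n + z²/(4n²)) / (1 + z²/n).

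- n = 30, p = 0.1, 0.2, 0.3: 0.222, 0.278, 0.312 (SAP: 0.22, 0.28, 0.31).
- n = 90: 0.126, 0.164, 0.186 (SAP: 0.13, 0.16, 0.19).
- At least one event at rate 0.05: 1 − 0.95³⁰ = 78.5% and 1 − 0.95⁹⁰ = 99.0% (SAP: 79% and 99%).

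These reproduce and are not in dispute. They describe the precision of a rate, not what the rate measures.

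**2. Simple masking arithmetic.** Let t be the event rate without supplements and f the share of events that supplements prevent. The observed rate is t(1 − f). The SAP gives neither, so both are assumed. Expected events in 30 infants:

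| t | f = 0 | f = 0.5 | f = 0.75 |
|---|---|---|---|
| 0.10 | 3 | 1.5 | 0.75 |
| 0.20 | 6 | 3 | 1.5 |
| 0.30 | 9 | 4.5 | 2.25 |

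**3. Simulation for potassium, all inputs assumed.** Mean potassium is 4.3, 4.0, 3.7 and 3.4 mmol/L for placebo and the three doses. Between-infant SD is 0.45, within-infant SD 0.35, with 8 samples in 28 days. A value below a trigger of 3.0, 3.2 or 3.5 is followed by a supplement that raises later values by 0.3 or 0.5. The triggers are modelling inputs, not clinical proposals.

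Without supplements, with u ~ N(0, 0.45²), P(any value ≤ 2.5) = 1 − E[{1 − Φ((2.5 − m − u)/0.35)}⁸]. This gives about 0.5%, 2.3%, 8% and 21% for placebo and the three doses.

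With supplements:

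- Top dose: 6–11% across the six trigger-gain settings. In 30 infants this is 0.21 × 30 ≈ 6 falling to about 2–3.
- Placebo: at or below 0.5%. The top-versus-placebo contrast shrinks from about 20 points to about 6–11.
- The order of the doses is kept in every setting. For trigger 3.2 and gain 0.5 the rates are about 0.2%, under 1%, 2.6% and 7–8%.

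Event or supplement, top dose versus placebo:

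| Trigger | Top dose | Placebo | Difference (points) |
|---|---|---|---|
| 3.0 | 57.7% | 5.4% | 52.3 |
| 3.2 | 72.5% | 11.4% | 61.1 |
| 3.5 | 88.5% | 27.2% | 61.3 |

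**4. What this composite is.** Every trigger lies above 2.5, so every infant with an event also has a supplement. The share with an event but no supplement is 0 in every setting, and the composite equals supplement use alone. Its larger contrast counts milder losses than the bands do; it is not a recovery of the prevented band events.

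**The case against.** The strongest reply is that the signal is already planned for. Table 14.3.4 reports supplement use by drug name and dose group, and under the simulation's own assumptions supplement use carries the whole 52–61 point contrast. This stands, and it limits the point: the losses are not hidden. What remains is the form of that table (by product, baseline use not separated, no joint reading). The simulation does not test the value of separating new starts, because no simulated infant has a baseline supplement.

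Second, under 9.1 the investigator may call any clinically significant change in routine laboratory results an AE, whatever the band. An infant without an event in table 14.3.2 may therefore still appear in the AE tables. This stands too, but that route is discretionary, and a value corrected early may be less likely to be reported.

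Third, listings 16.2.9.2 and 16.2.10 can be joined by infant. This is correct; only a prespecified joint display is absent.

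Fourth, section 7 calls the analyses exploratory or descriptive, so separate tables are a legitimate choice. They are, and nothing in 9.2 is contradictory on this point. The proposal improves a display and corrects no error.

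Fifth, an increase in supplement dose may not be derivable, because 9.3 mentions dose summaries only for caffeine. The fix allows for this.

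**Conclusion.** The point holds as a modest, cheap improvement. Table 14.3.2 understates dose-related electrolyte loss when replacement is given ahead of the band, and the understatement is probably largest at the dose causing most loss. Under the assumed inputs, the top-dose rate falls from about 21% to 6–11% and the dose order is kept. The direction rests on replacement following falling values; the size rests wholly on assumptions.

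A reader might infer that an unsafe dose could look safe, or that the dose trend could vanish or reverse. Arithmetic can be made to show this. True rates of 10%, 20% and 30% with prevented shares of 0, 1/2 and 2/3 all appear as 10% (3 of 30; 95% Wilson 3.5% to 25.6%). A prevented share of 0.75 at the top dose leaves 2.25 expected events against 3 at the lowest. Those shares were chosen to give that result. The SAP contains nothing to support them, and it tabulates supplement use by dose group. The documents support attenuation, not concealment or reversal.

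**What to change.** In 9.2 and table 14.3.2, keep the value-only rows. For each low-value electrolyte event with supplements recorded (hypokalemia, for example), add by dose group:

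- (a) infants with a new supplement of that electrolyte, IV or enteral, started after first dose, using the start date and indication collected under 9.3;
- (b) infants with the low-value event or such a new supplement.

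Supplements already running unchanged at baseline do not count. Count increases in dose only if supplement doses are captured; otherwise use new starts alone. State how combined salts, such as potassium chloride, are attributed.

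The cost is SAP wording, a mapping of products to electrolytes and derived variables from data already collected. No clinical management changes. Section 4.3 defers unmasking until the data are locked, so the rows can be specified while treatment is masked. The downside is that some new supplements are routine nutrition and that (b) counts milder losses than the bands. Both new rows are therefore read beside the value-only rows and do not replace them.

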3.2 Selection of Study Population

Premature infants (inpatient in neonatal intensive care units) will be randomized 3:1 to furosemide: placebo with increasing target doses of furosemide for each Cohort. There will be 40 randomized and dosed participants in each Cohort for a total of up to 120 participants.

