4.2 Interim Analyses

A masked interim safety analysis will be performed after completion of the safety follow up period of Cohort 1 participants, and again after completion of the safety follow up period of Cohort 2 participants to include data entered up to the cutoff time point (data from next Cohort will be included if entered before the cutoff time point). Enrollment will not be halted during the analyses. Halting may occur if analysis shows a positive finding. The number and percent of AEs and SAEs within each dose group will be summarized overall as well as by each Medical Dictionary for Regulatory Activities (MedDRA) system organ class and preferred term. BPD, nephrocalcinosis/nephrolithiasis, and hearing loss will be included in the summary. Also, laboratory adverse events will be tabulated by cohort.

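### The low-bicarbonate row of the laboratory event table (SAP 9.2) puts values from 12 to just under 14 mmol/L in both the AE and the SAE class

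*SAP*

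**What the plan says.** SAP section 9.2 has a laboratory event table with one column for adverse events and one for serious adverse events. The low-bicarbonate row reads "Low Bicarbonate levels(Bicarbonate) 12–14 mmol/L < 14 mmol/L". A typical low-side row, for comparison, is "Hypomagnesemia (Magnesium) 1.0–1.5 mg/dL < 1.0 mg/dL".

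The table feeds reported output. Section 9.2 states: "The laboratory events of interest will be summarized by dose groups". Section 13 lists table 14.3.2, "Summary of Laboratory Events by Dose Groups", supported by listings 16.2.9.1 and 16.2.9.2, which hold the measured hematology and chemistry values. Section 4.2 adds that at the masked interim analyses "laboratory adverse events will be tabulated by cohort".

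Section 9.1 defines seriousness by clinical outcome, as judged by the investigator or sponsor. It contains no laboratory limit and no rule for a value that meets both columns.

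There is also a labelling slip. The text says "The laboratory adverse events of interest are listed in Table 3", but the table itself is headed Table 7.

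**The concern.** The two columns look like consecutive bands: a milder range, then a more extreme one. For low bicarbonate the SAE limit sits at the upper edge of the AE band instead of the lower edge, so the SAE class swallows almost all of the AE class.

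Table 14.3.2 is built from measured values, so a programmer has only the printed limits to work from. If the summary separates AE-level from SAE-level events, as the two columns suggest, two programmers could put a bicarbonate of 13 mmol/L in different classes, or one could count it in both. Safety is the primary objective of this trial, so the laboratory classes should be unambiguous before treatment assignments are known.

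**Working it through.** **Inputs.** All limits come from the section 9.2 table. Group sizes come from the dose schedule in section 1.1 and from section 3.2 ("There will be 40 randomized and dosed participants in each Cohort for a total of up to 120 participants").

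**Step 1: the overlap.** The AE set is 12 ≤ x ≤ 14 and the SAE set is x < 14. Their intersection is 12 ≤ x < 14.

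| Value (mmol/L) | AE cell | SAE cell |
|---|---|---|
| 11.9 | no | yes |
| 12 | yes | yes |
| 13 | yes | yes |
| 13.9 | yes | yes |
| 14 | yes | no |
| 14.1 | no | no |

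**Step 2: is overlap the table's convention?** On the low side, a row overlaps if the SAE limit lies above the lower AE edge.

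| Low-side row | AE band | SAE limit | Relation |
|---|---|---|---|
| Sodium | 120–124 | < 120 | meet |
| Chloride | 80–90 | < 80 | meet |
| Potassium | 2.0–2.5 | < 2.0 | meet |
| **Bicarbonate** | **12–14** | **< 14** | **overlap** |
| Ionized calcium | 0.7–1.05 | < 0.7 | meet |
| Magnesium | 1.0–1.5 | < 1.0 | meet |
| Phosphorus | 1.0–3.0 | < 1.0 | meet |
| Platelets | 50–100 | < 50 | meet |

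Of the 12 high-side rows, 11 meet at the upper AE edge, including high bicarbonate (30–45, then > 45). The twelfth, high platelets, shows a gap because its SAE cell is garbled in the text as read; that is a separate matter. In total, 7 + 11 = 18 rows meet, 1 shows a gap and 1 overlaps.

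**Step 3: what each reading does.**
- SAE cell first: the AE class keeps only 14, and the printed lower edge of 12 has no function.
- AE cell first: the SAE class becomes x < 12, contrary to its printed limit.
- Both counted: 13 enters two classes while 11 enters one, so the less extreme value counts more often.

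**Step 4: how much of the AE band is affected.** The SAP does not give the reporting precision, so both cases are shown. In whole units the band holds 12, 13 and 14; 2 of 3 values are in both classes. To one decimal it holds 12.0 to 14.0, which is 21 values; 20 of 21 are in both. These are counts of possible values, not of infants.

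**Step 5: effect per affected infant.** Assume a split by class, one worst value per infant, full enrolment and a bicarbonate result for everyone. One infant moved between classes changes the serious-class percentage by 100/n:
- dose-level group, or placebo (3 × 10 = 30): 100/30 = 3.3 points
- interim cohort of 40: 100/40 = 2.5 points
- pooled furosemide (3 × 30 = 90): 100/90 = 1.1 points
- overall (120): 100/120 = 0.8 points

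The SAP gives no bicarbonate distribution, so the number of such infants cannot be computed.

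**The case against.** The strongest reply is that the row can be applied literally: a value of 13 is simply flagged in both columns, and any SAE is also an AE. The first half is true, and what fails is only the use of the columns as mutually exclusive classes, a split the SAP never states. The second half does not rescue the row, because values below 12 meet only the SAE cell. The classes are therefore not nested either, and no other row overlaps.

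The practical effect is also conditional. The percentages in step 5 are just 1/n and would hold for any single reclassified infant. Without a class split the effect is zero. Halting and escalation in section 4.1 count Serious Adverse Reactions, and the AE and SAE tables rest on seriousness judged under section 9.1; neither is shown to depend on this row. Section 7 calls the analyses exploratory or descriptive. All of this stands and limits the weight of the point.

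The protocol and case report forms are not at hand and could hold a tie-breaking rule, so its absence can be asserted only for the SAP. A digit altered in PDF extraction is conceivable, but the row reads cleanly; a look at the original page would settle that.

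**Conclusion.** The concern holds as a minor error. As printed, the low-bicarbonate cells overlap from 12 to just under 14 mmol/L, the only overlap in 20 rows, and nothing in the SAP resolves it. That is certain from the document; any effect on results is not. The effect is 3.3 points per affected infant in a group of 30, falling to 0.8 in the overall 120, if the assumptions in step 5 hold, and nil if events are counted without regard to class. The pattern of the other rows suggests that a limit was mistyped, but the document does not show which of the two cells is wrong.

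**What to change.** Before database lock and unmasking, the sponsor should confirm the intended limits and reconcile the two low-bicarbonate cells so that the AE and SAE bands no longer overlap. The source cited for the table, reference 4, should be checked as part of this. That citation needs verifying first: section 2.2.2.1 also uses number 4, for the BPD estimator, whereas the BPD prediction paper is number 5 in the reference list. The choice of limit is the sponsor's.

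In the same edit, make the table number in the text agree with the table heading. The cost is one row and one label; no new data are needed.
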